2.0 Synopsis

Sponsor;	AbbVie GK [name]
Title;	Assessment of clinical effectiveness and safety of adalimumab and high dose methotrexate in routine clinical practice (Combo study; Adalimumab with high dose MTX)
Short title;	HAWK study
Type of study;	Post-Marketing Observational Study (PMOS)
Product, dose, and administration form;	Humira® 40mg for S.C. Injection (generic name: adalimumab) 40 mg subcutaneous (s.c.) every other week
Project code;	JPN 12-01
Indication;	Rheumatoid arthritis (RA)
Study objectives;	
The primary objective of the study is to assess the clinical effectiveness of adalimumab in combination with high dose MTX (≥ 12 mg/week). The clinical effectiveness is measured by assessing the percentage of patients with the DAS28 score of < 2.6 at week 52.
 
The secondary objective of the study is to assess the clinical effectiveness of adalimumab in combination with high dose MTX (≥ 12 mg/week) by the following variables:
 
• Clinical Disease Activity Index (CDAI)• Simplified Disease Activity Index (SDAI)• The severity of functional impairment (HAQ)

- The health-related quality of life (EQ-5D)
- The severity of hand and foot mTSS used for assessment of radiographic joint damage.

Target parameters for safety evaluation of adalimumab + MTX are:

- The evaluation of safety and tolerability by the documentation and analysis of serious adverse events (SAEs) and adverse events (AEs).

Study population;	Adult patients (≥ 16 years) with early (≤ 2 years), MTX (≥ 12 mg/week) for at least 3 months before starting on adalimumab and DAS28-CRP > 3.2 , Bio Naive RA patients
Study design;	Single-arm, multi-center format, prospective cohort study
Treatment duration;	104 weeks
Methodology;	Disease Activity Score 28 (DAS28), Clinical Disease Activity Index (CDAI), Simplified Disease Activity Index (SDAI), Health Assessment Questionnaire (HAQ), EuroQol-5 Dimensions (EQ-5D), Radiographic joint damage (mTSS)
Total number of patients;	350 Patients
Adverse Events;	As reported by patients and diagnosed at visits
Data analysis plan;	
The general biometric approach consists of evaluation of changes by descriptive statistical methods, as well as of regression analysis of parameters influencing the clinical effectiveness and additional stratified group analysis.
 
Correlation between baseline visit and treatment visits:
 
• DAS28, CDAI, SDAI, HAQ, EQ-5D

(week 0, 12, 24, 52, 76, 104)

- Radiographic joint damage (mTSS)
(week 0, 52, 104)

Additionally, the strength of the relationship between the predictors and the parameters of clinical effectiveness will be determined. The impact of the variables determined by regression analysis on the therapeutic success will be illustrated by stratified group analysis. Two interim analyses are planned.

Planned recruitment phase;	September 2012 - December 2014
Planned study duration;	September 2012 - March 2017
Product manufacturer;	AbbVie GK

13.5 Times of Statistical Analyses29

14.0 Final Report and Publications29

15.0 References30

5.0 Introduction

Treatment of rheumatoid arthritis (RA) has advanced significantly after the introduction of biological agents and improved treatment recommendations. Current treatment guidelines for the management of RA advocate the use of an TNF-inhibitor in combination with MTX as first line biological therapy. Multiple studies have shown the synergistic effect of TNF-inhibitors and MTX. In February 2011, dosage regimens of methotrexate (MTX) were approved up to until ≤ 16 mg/week in Japan (2011 Japanese Guideline for MTX treatment with RA patient). Thus physicians may prescribe MTX in a maximum dose of ≤ 16 mg/week. Moreover MTX was also approved as first-line therapy in adult patients with RA.

MTX is a low-molecular-weight disease-modifying antirheumatic drug (DMARD) that has been demonstrated highly beneficial in inducing clinical remission, preventing the progression of bone destruction, improving quality of life (QOL), and ensuring durability and safety of treatment.¹⁻⁶⁾ On the basis of its usefulness in combination with other low-molecular-weight DMARDs and biologics, MTX is positioned as an anchor drug in the treatment of RA, and is one of the most commonly used low-molecular-weight DMARD in RA.⁷⁾ The benefits of MTX in combination with biological agents have been assessed in retrospective analyses of the data of post-marketing surveillance of biologics conducted prior to the approval of high-dose MTX treatment at ≥ 10 , ≤ 16 mg/week. Safety evaluation based on the incidence and patterns of adverse drug reactions (ADRs) by dose of MTX have revealed that the ADR profile does not differ significantly between lower and higher doses of MTX. Moreover, the efficacy of treatment appears better in patients receiving MTX at higher doses, which indicates a tendency toward dose-effect relationship. These results of retrospective analyses support the necessity of prospective studies to investigate the usefulness of treatment combining biological agents and high-dose MTX.

In the present prospective post-marketing observational study (PMOS), we will investigate the effectiveness and safety of treatment with adalimumab (Humira[®]) and high-dose MTX (≥ 12 mg/week).

6.0 Rationale

In Japan, Humira was approved on April 16, 2008 and launched in the market on June 18, 2008. As a condition of the approval, the Pharmaceuticals and Medical Devices Agency (PMDA) requested Abbott Japan to collect data on the safety and efficacy of adalimumab in all patients receiving the drug in order to take all necessary measures to ensure appropriate use of adalimumab. According to this requirement, Abbott Japan conducted an all-case survey of adalimumab in 7,740 Japanese patients with rheumatoid arthritis (RA) receiving the drug during the period between June 2008 and October 2010. The results of a recent retrospective data analysis of the all-case survey of Japanese patients with RA suggested that the effectiveness of adalimumab in bio-naïve patients with RA was more efficacious when they receive adalimumab in combination with MTX at a dose of ≥ 10 mg/week. We thus designed a prospective special investigation of ADA + MTX ≥ 12 mg/week assessment for DAS28, mTSS and HAQ in bio-naïve and early patients with RA and following within the current labeling in Japan.

7.0 Study Objective (s)

In daily clinical setting, patients with RA who receive adalimumab (Humira[®]) and high-dose MTX (≥ 12 mg/week) will be observed prospectively and the effectiveness will be assessed by DAS28 and mTSS. In addition the safety of the combination of adalimumab and high dose MTX will be assessed in terms of the incidence and pattern of the occurrence of adverse events.

The primary objective of the study is to assess the clinical effectiveness of adalimumab in combination with high dose MTX (≥ 12 mg/week). This will be measured by assessing the percentage of patients with the DAS28 score of < 2.6 at week 52.

The secondary objective of the study is to assess the clinical effectiveness of adalimumab in combination with high dose MTX (≥ 12 mg/week) by assessing the proportion of patients with a change in the following variables from baseline to week 104:

- Clinical Disease Activity Index (CDAI)
-

- Simplified Disease Activity Index (SDAI)
- The severity of functional impairment (HAQ)
- The health-related quality of life (EQ-5D)
- The inhibition of structural progression will be assessed by measuring the modified Van der Heijde Total Sharp Score (mTSS).

The safety profile will be assessed by measuring the following variables:

- All serious adverse events (SAEs) and adverse events (AEs)

7.1 Investigational Plan

7.2 Selection of Study Population

The study population will consist of adult patients (≥ 16 years) with early RA (disease duration of RA ≤ 2 years) who have failed other anti-rheumatic drugs (with prior MTX). Patients who have been previously treated with biologics (including TNF inhibitors others) cannot be included in the PMOS. The inclusion and exclusion criteria adhere to the approved label as stated in the Japan Summary of Product Characteristics (SPC) “Interview-form” for adalimumab. Investigators will fully explain the PMOS and obtain informed consent from each patient who is to receive adalimumab for the treatment of RA. Patients to be included will be informed about the PMOS and the use of their anonymous data.

7.2.1 Inclusion Criteria

The subjects of this study are patients with a diagnosis of RA and to whom adalimumab is prescribed as part of their normal treatment of RA. All subjects should be satisfying the following conditions.

- 1) Disease duration of RA ≤ 2 years
 - 2) MTX administration ≥ 3 months prior to starting adalimumab
 - 3) Dose of MTX ≥ 12 mg/week
-

4) DAS28-CRP >3.2

7.2.2 Exclusion Criteria

- 1) Patients who have been previously treated with biologics (including TNF inhibitors others)

7.3 Number of Patients to be Enrolled

The primary endpoint of this study is the proportion of subjects who achieve DAS28 (CRP) remission (DAS28 <2.6) after 52 weeks of adalimumab + high dose MTX. Based on data from another trial assessing the effectiveness of adalimumab in daily clinical practice, the following power calculation was done⁹⁾. With a significance level of 0.05 (two-sided) and a power of 0.90 (1-β), 350 subjects are required to detect an expected remission rate, i.e., the percentage of patients with the DAS28 score of <2.6 at week 52.

7.4 Investigator Selection Criteria

The data for this PMOS will be collected from rheumatology outpatient departments and office based rheumatologists that routinely treat patients with RA in Japan.

Physicians from about 100 sites which are spread across all of Japan will participate in this PMOS.

Principal Investigator:

Name; [name]. [name]

Institution; University of Occupational and Environmental Health

Address; [name]

7.5 Study Duration

- 1) The duration of the whole PMOS is estimated to be about 4 years.

- Study start: September 2012
-

- Recruiting phase: September 2012 - December 2014
 - Data completion: January 2018
 - End of study: The date on which statistical analysis dataset for Clinical Study Report becomes available
 - Data analysis and final report: April 2018 – October 2018
- 2) For each individual patient, the PMOS starts with the enrollment at the beginning of the treatment with adalimumab.
- Observation period
 - 104 weeks (or discontinuation of this study)
 - Discontinuation of this study
 - Patients within 52 weeks into this study: When adalimumab treatment is discontinued.
 - Patients after 52 weeks into this study: When any biologics other than adalimumab is administered.

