7.6 Study Conduct

7.6.1 Schedule of Observations

This PMOS will be a single-arm, multi-center, prospective cohort study.

Non-interventional studies are one of several methodical instruments to collect information on drugs available on the market. Their defining characteristic is the lack of influence on the relationship between individual physicians and patients in respect to determining indication as well as choice and conduct of the treatment, while at the same time allowing for the structured and systematic collection of treatment data (see also Section 6 “Rationale”). Adalimumab must not be prescribed for the purpose of including a patient in this PMOS.

Patients will be informed about the type of therapy, alternate therapies, and risks, and they have to provide informed consent before the start of adalimumab therapy. Before enrollment in the PMOS, the patients will be made anonymous. AbbVie GK will only receive access to anonymous data. AbbVie GK can only identify the patients via their patient number.

The documentation consists of patient self-assessments as well as assessments by the physician. The following table provides an overview of the study visits with corresponding study activities (Table 1 “Study Schedule”).

Table 1. Study Schedule

Activity	Visit (Week)					
	0	12	24	52	76	104*
Patient Background	✓					
Inclusion / Exclusion criteria	✓					
Previous RA therapies	✓					
Concomitant diseases and therapies	✓	✓	✓	✓	✓	✓
Current adalimumab therapy	✓	✓	✓	✓	✓	✓
Current RA therapies	✓	✓	✓	✓	✓	✓
Effectiveness						
• DAS28	✓	✓	✓	✓	✓	✓
• CDAI	✓	✓	✓	✓	✓	✓
• SDAI	✓	✓	✓	✓	✓	✓
• HAQ	✓	✓	✓	✓	✓	✓
• EQ-5D	✓	✓	✓	✓	✓	✓
• mTSS (X-rays of Hands and Feet)	✓			✓		✓
Adverse Events		✓	✓	✓	✓	✓

* Week 104 or last visit

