7.6.4 Study Medication

This is a non-interventional observational study with adalimumab. Adalimumab is used according to the approved label for rheumatoid arthritis and is prescribed by the attending physician. AbbVie GK does not provide any study medication. HUMIRA[®]-injection is available as ready-to-use syringes (injector, pre-filled) and includes 40 mg adalimumab. The recommended dose of adalimumab for adult patients with RA is 40 mg sc every other week.

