9.3 Serious Adverse Event Collection Period

Serious adverse events will be reported to AbbVie GK from the time the physician obtains the patient's authorization to use and disclose information (or the patient's informed consent) until the end of the PMOS (week 104 or discontinuation of this study).

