12.0 Case Report Forms

All data specified in Section 8.5 "Study Conduct" will be collected on paper forms (CRF). For each visit, the CRF includes forms to be completed by the physician as well as forms to be completed by the patient. Each center receives a folder with all documents and forms necessary for the baseline and follow-up documentation of contract number of cases.

Any observation of an adverse event in the time period up to 104 weeks (or discontinuation of this study), beginning with the initiation of adalimumab therapy, is to be documented on the CRF. If the event fulfills the serious criterion (Serious Adverse Event), the "Serious Adverse Event Report" form is to be completed additionally.

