Treatment period (day) Completion date of treatment *Per record	
It should be between the start date of Humira treatment and the completion date of treatment per treatment record.
 
When the completion date of treatment in the information on the previous treatment within the same CRF and the start date of treatment in the information on the relevant treatment are the same date, the completion date of treatment in the information on the previous treatment should be - 1 day.
 
The records with the dose of 0 mg should be excluded from the analysis.

Dosing intervals (day) *Per record	Biweekly should be 14 days, once in three weeks should be 21 days, and once in four weeks should be 28 days, respectively.
Total number of doses	The total after calculating the number of doses per record by rounding up the first decimal place should be taken for treatment period (day)/dosing intervals (day).
Patients who discontinued Humira treatment	If the final fixed CRF is the first or second CRF, the patients should be handled as the patients with a description in the “treatment discontinuation” column in the final CRF. If the final fixed CRF is the third CRF, the patient should be handled as the patients with a description of the completion date of treatment in the final record of the “Humira treatment status” column in the final CRF.
Patients who are continuing Humira treatment	If the final fixed CRF is the first or second CRF, the patients should be handled as the patients without a description in the “treatment discontinuation” column in the final CRF. If the final fixed CRF is the third CRF, the patient should be handled as the patients with a description of “continuing” in the final record of the “Humira treatment status” column in the final CRF.
Date of treatment discontinuation	In patients who discontinued Humira treatment, the completion date of Humira treatment should be the date of discontinuation.
Low body weight	Patients with body weight of < 30 kg.
Date of survey discontinuation	It should be the date of survey discontinuation described in the third CRF. It should be the start date of treatment with other biological products, or the older date among the last follow-up date.
AE follow-up period	It should be between the date of initial Humira treatment and the date of initial Humira treatment + 755 days.

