Reason for discontinuation (third CRF)	Occurrence of AEs, symptom improved, inadequate response, patient refused treatment with Humira, others (pregnancy/desire for pregnancy, others), undescribed
Reason for survey discontinuation	Administration of biological products other than Humira, failed to visit hospital, others, undescribed

<Efficacy endpoints>

Data	Layer separation	
DAS28-4ESR	High Moderate Low Remission	> 5.1 > 3.2 and ≤ 5.1 ≥ 2.6 and ≤ 3.2 < 2.6
DAS28-4CRP	High Moderate Low Remission	> 5.1 > 3.2 and ≤ 5.1 ≥ 2.6 and ≤ 3.2 < 2.6
CDAI	High Moderate Low Remission	> 22.0 > 10.0 and ≤ 22.0 > 2.8 and ≤ 10.0 ≤ 2.8
SDAI	High Moderate Low Remission	> 26.0 > 11.0 and ≤ 26.0 > 3.3 and ≤ 11.0 ≤ 3.3
HAQ-DI	High Moderate Low Remission	> 1.5 > 1.0 and ≤ 1.5 > 0.5 and ≤ 1.0 ≥ 0 and ≤ 0.5
mTSS	Change (≤ 0) Change (≤ 0.5) Change (≤ 1.0)	Change ≤ 0 Change ≤ 0.5 Change ≤ 1.0
Bone erosion score	Change (≤ 0) Change (≤ 0.5) Change (≤ 1.0)	Change ≤ 0 Change ≤ 0.5 Change ≤ 1.0
Joint space narrowing score	Change (≤ 0) Change (≤ 0.5) Change (≤ 1.0)	Change ≤ 0 Change ≤ 0.5 Change ≤ 1.0

*Hereafter, “complete remission” refers to “Remission” in the above table.

12. Handling of data on test/evaluation time

For data entered at each timing of efficacy evaluation excluding mTSS, bone erosion score and joint space narrowing score, the acceptability of data by timing should be judged based on the acceptable range of the timing. The acceptable range of the timing is shown in the table below.

If there is more than one data within the acceptable range of the timing, the data on the closest date to the reference date should be adopted. If there is more than one data within the acceptable range of the timing with the equal number of days from the reference before and after the reference date respectively, the data before the reference date should be adopted.

When evaluating efficacy regarding administration of Humira, it should follow the following provision for the data included in the following acceptable range.

- The data up to the date of final Humira treatment + 28 days should be tabulated.

However, the date of final Humira treatment +28 days is later than the date of survey discontinuation, the data up to the date of survey discontinuation should be tabulated.

This date is called [final evaluation date] in the following.

Timing and period category	Handling of data

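### For patients who stop adalimumab in year 1, AE/SAE collection closes at the stop with no post-treatment window, yet the SAP plans to tabulate their later events up to day +755

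*Protocol*

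**What the plan says.** **When the study ends for a patient.** Protocol 7.5 has two rules. In year 1: "Patients within 52 weeks into this study: When adalimumab treatment is discontinued". Later: "Patients after 52 weeks into this study: When any biologics other than adalimumab is administered". Otherwise observation runs to 104 weeks.

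**When AE and SAE collection ends.** Protocol 9.3 has SAEs reported "until the end of the PMOS (week 104 or discontinuation of this study". Protocol 12.0 uses the same end point for the CRF: "Any observation of an adverse event in the time period up to 104 weeks (or discontinuation of this study". Neither section adds a period after treatment.

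**Other places where events may be recorded.** The final column of Table 1 in Protocol 7.6.1, which includes adverse events, is footnoted "Week 104 or last visit". Section 7.6.2 also lists a last visit that records (S)AEs and the reason for stopping. How long after the stop this visit takes place is not stated.

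**SAP.** Section 10.1 defines the AE follow-up period for every patient as the first Humira date to that date +755 days, with no cut at treatment stop, and 10.2 excludes only events outside that period. Section 12 has an onset category for events after treatment completion. Tables 5.3.1 and 5.3.2 in 13.2 split events into during and after treatment for patients who discontinued. By 10.1 that group includes patients whose last fixed CRF is the first or second, that is, year-1 stoppers. On dating, 10.1 says: "In patients who discontinued Humira treatment, the completion date of Humira treatment should be the date of discontinuation". For efficacy, section 12 says: "The data up to the date of final Humira treatment + 28 days should be tabulated".

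**The concern.** Safety of the combination is a stated objective (Protocol 7.0), and SAP 3.1 says the results feed regulatory reporting and reexamination. SAP 11 lists occurrence of AEs among the reasons for stopping, so some patients stop while a reaction is emerging. The protocol's own AE definition (9.1.1) covers events arising from drug withdrawal. For a year-1 stopper, formal collection closes just as such events become possible.

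The loss runs in one direction and is differential. It can only lower counts, and it applies to patients who stop before week 52 but not to those who stop after. The SAP's post-treatment columns would be filled mainly by year-2 stoppers. A reader who sees few post-treatment events among year-1 stoppers could take this as reassurance when it reflects the collection window.

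**Working it through.** **1. The collection rules side by side.**

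| Patient | Protocol collection ends | SAP AE period ends |
|---|---|---|
| Stops in weeks 0–52 | at discontinuation | day +755 |
| Stops after week 52 | another biologic, or week 104 | day +755 |
| Does not stop | week 104 (day 728) | day +755 |

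Two illustrations, neither patient starting another biologic. A stop on day 140 gives 0 days of formal off-drug collection under the protocol, against a nominal 755 − 140 = 615 days in the SAP. A stop on day 400 gives 728 − 400 = 328 days under the protocol. Even for a patient who never stops, the SAP period runs 755 − 728 = 27 days past the protocol's. The SAP period is thus not derived from what sites are asked to report.

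**2. The plan's own figure, source of the 50%.** Inputs: reference rate 42.7%, expected rate 55%, two-sided alpha 0.05, power 0.90 (Protocol 13.1, SAP 4.3).

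n = [1.960·√(0.427·0.573) + 1.282·√(0.55·0.45)]² / 0.123² = 170.7, rounded up to 171. This reproduces the stated 171. Then 171/(1 − 0.50) = 342, as stated, with the target set at 350. None of these figures is affected by this point.

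The 50% is extrapolated from 32% dropout at 24 weeks. A constant hazard would give 1 − 0.68^(52/24) = 56.6% at week 52, so 50% is in line with its source.

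**3. Size of the gap, upper reading.** Assume that all dropouts are drug stops, every stop is dated at the last injection, and nothing after it is recorded.

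- Stoppers: 350 × 0.50 = 175.
- On-drug time in year 1 with constant hazard: 350 × (1 − 0.5)/ln 2 ≈ 252 patient-years.
- Protocol 7.6.4 states: "The recommended dose of adalimumab for adult patients with RA is 40 mg sc every other week". One dosing interval is therefore 14 days: 175 × 14/365.25 = 6.7 patient-years. Missed share at an equal event rate: 6.7/(252 + 6.7) = 2.6%.
- The SAP's 28-day efficacy window: 175 × 28/365.25 = 13.4 patient-years; 13.4/(252 + 13.4) ≈ 5%.

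Range over the stopping proportion:

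| Stop in year 1 | Patients | 14 days (patient-years) | 28 days (patient-years) |
|---|---|---|---|
| 32% | 112 | 4.3 | 8.6 |
| 50% | 175 | 6.7 | 13.4 |
| 56.6% | 198 | 7.6 | 15.2 |

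**4. What the dating rule does to this.** Neither document says whether the completion date is the last injection or the decision to stop. The SAP's planned completion dates for continuing patients are +167, +363 and +727 days. On a 14-day schedule from day 0, the injections before these fall on days 154, 350 and 714, each 13 days earlier. There, completion means the end of the dosing interval. If actual stops are dated in the same way, or at a later visit, most or all of the 14 days is already inside the protocol window.

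**The case against.** The strongest reply is that non-collection is not established. The SAP follows AEs to day +755 for everyone and plans post-treatment tables for patients who discontinued. It accepts efficacy data to 28 days after the final Humira date, so it expects some assessments after the stop. A last visit records AEs, and a visit after the final injection would pick up events since that injection. SAP 10.2 builds the AE data by matching CRF data with safety information data, so the CRF is not the only source. Events with onset before the stop are already inside the window. The study is non-interventional and documents what routine care provides.

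Much of this stands as a limit on size. A reader might infer that events after a year-1 stop are never collected and cannot be recovered. The documents do not support that: the last visit and the matching are both possible routes, although neither the timing of the visit nor the reach of the matching is stated. A reader might also infer that half the cohort loses the full dosing interval. The 50% is assumed dropout, not assumed drug stops, and it may include patients who simply failed to attend.

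The SAP's day +755 does not dispose of the point. It is a tabulation rule; Protocol 9.3 and 12.0 tell sites what to report. A SAP cannot supply events that sites were not asked for, and the mismatch is itself part of the problem.

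**Conclusion.** The point holds as a gap in systematic collection together with a conflict between protocol and SAP. Year-1 stoppers have no stated post-treatment window, later stoppers do have off-drug observation, and the SAP tabulates as though both were followed to day +755.

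On the upper reading the size is about 2.6% of year-1 events for a 14-day gap and about 5% for 28 days. It rests on four assumptions: constant dropout hazard, equal event rates before and after the stop, all dropouts being drug stops, and stops dated at the last injection. If stops are dated later, the loss is smaller and could be nil for the 14 days. A reader might go further and put the loss at 10% to 14%. That needs an event rate two to three times higher just after stopping, for which the documents give no basis.

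The case for changing the plan is the differential ascertainment on a stated safety objective more than the size of the loss. The fix is cheap and should be made.

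**What to change.** 1. In Protocol 7.5, 9.3 and 12.0, separate AE/SAE collection from the end of effectiveness observation. For patients who stop within 52 weeks, collect AEs and SAEs known to the physician until 28 days after the last recorded adalimumab dose, which is the length of the SAP's own efficacy carry-over window.
2. State in both documents whether the discontinuation or completion date is the last injection or the decision to stop.
3. In SAP 10.1, 10.2, 12 and 13.2, align the AE follow-up period and the post-treatment tables with each patient's actual collection window, and show year-1 and later stoppers separately. Without this step the 28-day limit would still contradict day +755.

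**Cost.** One added reporting period for early stoppers, with no extra visit because data come from routine care, and slightly higher event counts. Patients lost to follow-up will yield little. Only data collection and tabulation change, not treatment.

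Protocol 7.5 puts the end of recruitment at December 2014 and data completion at January 2018. If collection can no longer be extended, items 2 and 3 remain possible, and the report should state the limitation beside the post-treatment tables.
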